Steroid resistance, as documented in cases of severe asthma, is associated with increased expression of the glucocorticoid receptor (GR)- β , which is an alternative splicing isoform and dominant-negative regulator of the GR- α ¹⁴. The abundance of GR- α mRNA is higher than GR- β mRNA in all normal tissues and cells. Normally, default splicing pathway leads to GR- α , while the alternative

splicing pathway that leads to GR- β is minimally activated ¹⁵. The latter pathway, however, seems to be upregulated in severe asthmatic patients ¹⁶. In chronic inflammatory diseases like asthma, upregulated blood levels of inflammatory cytokines can participate in glucocorticoid resistance and impaired GR function by modulating its translocation, DNA binding, and GR phosphorylation status [18].

As data from observational studies suggested a better control of asthma following restoration of VitD levels.

Hypothesis:

Correcting VitD levels in adult asthmatic patients could enhance steroid responsiveness by regulating blood GR- α /GR- β ratio levels.

Primary Out comes:

1. To find out the top pathways regulate Vitamin D

identify VitD targeted enriched pathways, we analyzed Comparative Toxicogenomics .Enriched Ontology Clustering for the identified genes was performed using the Metascape (a web-based tool used for comprehensive gene list annotation and analysis resource)Database from thousands of experiments.[Time Frame: 8 weeks]

2. To examine asthma severity in relation to steroid receptors genes [Time Frame: 8 weeks]

3. study the effect of vitamin D on GR- α receptor [Time Frame: 8 weeks]

4. study the effects of Vitamin D on cytokines. [Time Frame: 8 weeks]

Inclusion Criteria:

- Diagnosis of asthma
- age group between 18 and 65 years
- low level of 25-hydroxyvitamin D3 (25 D3) level less than 20ng/mL

Exclusion Criteria:

- smoker patients
- less than 18 years old
- patient on Vitamin D supplementation already

Materials and Methods

In silico identification of top genes regulated by vitamin D supplementation

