Using Comparative Toxicogenomics Database to identify the top genes influenced by vitamin D supplementation in thousands of experiments. One hundred five genes with at least five documented interactions with VitD were identified. Moreover, to explore if the identified genes are sharing common pathways, Enriched Ontology Clustering for the identified genes will be performed using the Metascape (a web-based tool used for comprehensive gene list annotation and analysis resource).

In silico determination of effect of vitamin D treatment on the expression of NR3C1 and NR3C2 in monocytes, macrophages, and dendritic cells

In order to investigate the effect of VitD supplementation on the mRNA expression of NR3C1, NR3C2 and VDR, publicly available datasets (GSE52819, GSE13762, GSE56490) will be explored as they were designed to examine the global transcriptional effect of VitD supplementation on monocytes, macrophages, and dendritic cells.

In silico determination of the mRNA expression levels, and correlations, of NR3C1, NR3C2, and VDR in the blood of asthmatic patients compared to healthy controls

We will extract from publicly available datasets (GSE69683) with a large number of participants and their detailed clinical information. To find Gene expression profiling of blood from these groups was analyzed, and the gene expression of GR (NR3C1 and NR3C2) which was determined.

Patients

To do double-blinded, randomized, placebo-controlled study of VitD supplementation on 45 asthmatics with VitD deficiency will be performed. Moderate to severe asthmatics between 18 and 65 years of age who had clinician-diagnosed asthma with 25-hydroxyvitamin D3 (25 D3) level less than 20ng/mL at the screening visit will be recruited at the Rashid Hospital, Dubai, U.A.E., and the Zayed Military Hospital, Abu Dhabi, U.A.E.

mRNA expression and cytokine expression

Whole blood will be collected in PAXgene tubes (Qiagen, Germany) for the isolation of cellular RNA. Blood specimens will be assessed for mRNA expression of Glucocorticoid receptor (GR- β and

GR- α) using qRT-PCR. Bioplex multiplex immunoassay (BioRad, CA, USA) will use to assess the protein expression of IL-17A, IL-17-F, IFN- γ , IL-4, IL-5 and TNF- α in serum obtained from patients before and after treatment.

Statistical Analysis

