when compared to baseline level. A significant increase was observed following treatment with VitD compared to pre-treatment levels (1.89 ± 0.56 , 5.34 ± 1.40 , respectively; $p<0.05$) (Figure 4A). Moreover, there was a significant increase in GR- α expression in patients who received VitD compared to those who received the placebo control (5.34 ± 1.40 versus 1.64 ± 0.76 -fold; $p<0.05$). Interestingly, no change in GR- β expression was observed following treatment with VitD (1.49 ± 0.27 versus 1.30 ± 0.25) (Figure 4B). Relatively, the GR- α /GR- β ratio increased significantly following VitD supplementation compared to pre-treatment levels (3.58 ± 0.83 folds; $p<0.05$); or patients who received a placebo (Figure 4C).

[figure not shown]

Figure 4: Vitamin D treatment increases the expression of GR- α with no effect on GR- β .

Asthmatic subjects were treated with 50,000 IU of vitamin D orally or placebo for eight weeks. Blood specimens obtained following 8 weeks of treatment were analyzed for mRNA expression of GR- α (A), GR- β (B) using RT qPCR and the ratio of GR- α /GR- β was calculated (C). * $p<0.05$

Vitamin D supplementation downregulated the blood levels of IL-17 and IL-4 cytokines in asthmatic patients

The effect of VitD supplementation on the blood levels of asthma related pro-inflammatory cytokines was then determined (Figure 5)²⁰. Blood levels of IL-17A, IL-17F, IFN- γ , IL-4, IL-5, and TNF- α were determined before and after VitD supplementation using ELISA assay (Figure 5). VitD preferentially suppressed the blood levels of IL-17F cytokine ($p=0.04$) without affecting IL-17A; while there was no significant difference in the placebo group ($p=0.17$). A decrease in blood IL-4 cytokine levels was observed following treatment, however, not to a significant level ($p=0.07$). No significant effect of VitD supplementation was observed on the rest of the cytokines tested.

References

- 1 Palacios, C. & Gonzalez, L. Is vitamin D deficiency a major global public health problem? *J Steroid Biochem Mol Biol* **144 Pt A**, 138-145, doi:10.1016/j.jsbmb.2013.11.003 (2014).

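### The cytokine heading claims that vitamin D lowered IL-17 and IL-4, but its own paragraph supports only IL-17F, nominally, and the readable text gives no comparison with placebo

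*Combined protocol and SAP*

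**What the plan says.** The Primary Outcomes list has as item 4: "study the effects of Vitamin D on cytokines", at 8 weeks. The section on mRNA and cytokine expression names six cytokines (IL-17A, IL-17F, IFN-γ, IL-4, IL-5, TNF-α), to be measured "in serum obtained from patients before and after treatment". The Statistical Analysis section plans t-tests and one-way ANOVA with a 0.05 threshold. It does not say which groups are compared, whether tests are paired, or how several cytokines are handled.

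The Results heading for this outcome is "Vitamin D supplementation downregulated the blood levels of IL-17 and IL-4 cytokines in asthmatic patients". The paragraph under it says:

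- Levels "were determined before and after VitD supplementation using ELISA assay".
- IL-17: "VitD preferentially suppressed the blood levels of IL-17F cytokine ($p=0.04$) without affecting IL-17A; while there was no significant difference in the placebo group ($p=0.17").
- IL-4: "A decrease in blood IL-4 cytokine levels was observed following treatment, however, not to a significant level ($p=0.07").
- The others: "No significant effect of VitD supplementation was observed on the rest of the cytokines tested".

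The GR-α paragraph in the same part of the Results does make a between-arm comparison. It reports a significant increase in "expression in patients who received VitD compared to those who received the placebo control" (5.34 versus 1.64, p<0.05).

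**The concern.** There are three separate points, in decreasing order of certainty.

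1. **Heading against text.** The heading names two cytokines as lowered by treatment. By the document's own threshold one of them (IL-4) is not significant. The other is named without its isoform, so the claim takes in IL-17A, which the text reports as unaffected.
2. **No between-arm result.** A randomised, placebo-controlled trial supports a treatment claim through the difference between arms. A result below 0.05 in one arm and above 0.05 in the other is not a test of that difference. On the natural reading, the cytokine paragraph offers only such a pair.
3. **Six tests, no ranking.** Six cytokines share one primary outcome, each judged at 0.05, with no adjustment and no statement that the p-values are nominal. This is the lesser point.

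A reader who takes the heading as the result of a primary outcome will believe that effects on IL-4 and on IL-17 as a whole have been established.

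**Working it through.** **Step 1: the heading against its paragraph.** No assumption is needed here.

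| Cytokine | Heading | Paragraph | Below 0.05? |
|---|---|---|---|
| IL-4 | lowered | numerical fall, p=0.07 | no |
| IL-17A | lowered (IL-17, no isoform given) | unaffected | no |
| IL-17F | lowered (IL-17, no isoform given) | p=0.04 | yes, nominally |
| IFN-γ, IL-5, TNF-α | not named | no significant effect | no |

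One cytokine of six is below the threshold.

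**Step 2: what the two within-arm p-values imply between arms.** The published p-values cannot be reproduced, because the text gives no cytokine means, SDs or numbers per test. The following is an illustration. It assumes two-sided paired t-tests, complete cytokine data, and that p=0.17 refers to IL-17F. Two sets of arm sizes (vitamin D/placebo) are used because the document gives two: 34/20 in Table 1 and 23/22 in the Figure 3 legend.

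Standardised mean change in one arm: d = t(1−p/2, n−1)/√n.

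- 34/20: vitamin D 2.138/√34 = 0.367; placebo 1.426/√20 = 0.319.
- 23/22: vitamin D 2.183/√23 = 0.455; placebo 1.421/√22 = 0.303.

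With equal SDs of change, the between-arm t is the difference in changes divided by √(1/n₁+1/n₂), on n₁+n₂−2 degrees of freedom. The divisor is 0.282 (34/20) or 0.298 (23/22). The 95% CI half-width is 0.565 or 0.601 SD.

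| Placebo change | Arms | Difference (SD) | 95% CI | t | p |
|---|---|---|---|---|---|
| also fell | 34/20 | 0.367−0.319 = 0.05 | −0.52 to 0.61 | 0.17 | 0.87 |
| also fell | 23/22 | 0.455−0.303 = 0.15 | −0.45 to 0.75 | 0.51 | 0.61 |
| rose | 34/20 | 0.367+0.319 = 0.69 | 0.12 to 1.25 | 2.43 | 0.018 |
| rose | 23/22 | 0.455+0.303 = 0.76 | 0.16 to 1.36 | 2.54 | 0.015 |

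*Rounding of the published p-values* (0.035–0.045 and 0.165–0.175). Same direction: 0.83–0.90 (34/20) or 0.57–0.65 (23/22). Opposite direction: 0.016–0.021 or 0.013–0.017.

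*Unequal SDs.* Let r be the placebo/vitamin D ratio of SDs of change, from 0.5 to 2. The Welch test uses difference d₁∓r·d₂, variance 1/n₁+r²/n₂ and Satterthwaite degrees of freedom. Over both sets of arm sizes p runs from 0.20 to 1.00 (same direction) and from 0.013 to 0.046 (opposite). In the same-direction case the two mean changes coincide at r = 0.367/0.319 = 1.15 (34/20) or 0.455/0.303 = 1.50 (23/22).

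The text does not state the direction of the placebo change, and the answer turns on it.

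**Step 3: multiplicity over six cytokines.**

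- Chance of at least one false positive if the tests are independent: 1−0.95⁶ = 0.265, and less if they are positively correlated.
- IL-17F has the smallest p if the four unreported values are at least 0.05. Its adjusted p is then 6×0.04 = 0.24 (Bonferroni or Holm) or 1−0.96⁶ = 0.22 (Šidák).
- Hochberg gives at least 0.07, because the largest p is at least 0.07. Benjamini–Hochberg gives at least 0.05×6/5 = 0.06.
- Closed tests that combine p-values depend on the four unreported values and also assume independence. With all four equal to x, the adjusted p (Fisher/Stouffer) is 0.040/0.040 at x=0.05, 0.047/0.040 at x=0.20, 0.098/0.054 at x=0.30 and 0.29/0.22 at x=0.50.

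**The case against.** The strongest reply is that nobody who reads on is deceived. The paragraph directly under the heading gives the IL-4 p-value, calls it non-significant and says IL-17A did not change. The heading does not use the word significant, IL-4 did fall numerically, and IL-17 can be read as a family name covering IL-17F. All of this is true, and it makes the fault one of overstatement, not of reversed direction. It does not rescue the heading, which attributes the changes to treatment as a finding on a primary outcome when the authors' own criterion does not support that for IL-4 or IL-17A.

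The second reply is that Figure 5 is missing from the available text and may show the between-arm test. That stands, and the second point is limited accordingly: it concerns the readable text only, and that p=0.04 is a before-after result and p=0.17 belongs to IL-17F are readings, not stated facts. The heading conflict does not depend on the figure.

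Third, baseline adjustment is not in the plan, and a t-test on change or on week-8 values would also compare the arms. Also true. The essential request is the between-arm estimate; adjusting for baseline is the better way to obtain it.

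Fourth, the illustrative p-values run from near 0.01 to 1.00 and so do not measure an effect. They are not meant to: the width of that range is the point. Finally, multiplicity is a general gap in the Statistical Analysis section, so it is carried here only as a recommendation.

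**Conclusion.** The concern holds. That the heading overstates its own paragraph is certain from the text: one of six cytokines is below 0.05, and the heading's claim is wrong for IL-4 and IL-17A.

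That no vitamin D versus placebo cytokine result is given holds for the readable text, with moderate confidence about what the p-values refer to. Under the stated assumptions they are compatible with practically no difference between arms or with a nominally significant one. The between-arm effect is undetermined; it has not been shown to be absent.

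The IL-17F result is nominal. It does not survive Bonferroni, Holm, Šidák, Hochberg or Benjamini–Hochberg at 0.05. Some combination-based closed tests would keep it if the unreported p-values were small.

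**What to change.** **Must:** reword the heading to say that no effect was shown on IL-4 or IL-17A and that IL-17F was nominally lower within the vitamin D arm, unless the between-arm test supports more.

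**Must:** for each of the six cytokines, report the week-8 vitamin D minus placebo difference adjusted for the baseline value (for example by ANCOVA), with its 95% CI and the number analysed per arm. Keep before-after tests for description. If Figure 5 already contains a between-arm test, state its result in the text. Say which cytokine p=0.17 belongs to and in which direction placebo moved.

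**Should:** either label the six p-values nominal and unadjusted, or apply one named multiplicity method, labelled post hoc.

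**Cost:** a changed heading and a small re-analysis. No new samples are needed if serum was collected before and after treatment in both arms, as the plan implies; the Results do not show placebo values for every cytokine, so this needs confirming. The claim will become weaker. With complete data in 45 to 54 patients the intervals will be wide, about ±0.57 to ±0.60 SD of change before baseline adjustment, and wider if data are missing.

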Standard statistical t-tests and one-way ANOVA will be performed to test for statistical significance between data groups using GraphPad Prism 8 (GraphPad, San Diego, CA, USA). $p < 0.05$ was considered significant.

To whom it may concern

Date : 15/06/2020

Subject : Vitamin D Regulates the Expression of Glucocorticoid Receptors in Blood of Severe Asthmatic Patients

I am [name] ,Principle investigator for the study (Vitamin D Regulates the Expression of Glucocorticoid Receptors in Blood of Severe Asthmatic Patients) . I am confirming that the results is relevant to the study in the record.

Results :

Top Vitamin D regulated pathways are involved in response to Steroids

To identify VitD targeted enriched pathways, we analyzed Comparative Toxicogenomics Database from thousands of experiments. Interestingly, the top enriched pathways regulated by VitD were involved in several metabolic and inflammatory processes including response to steroids, lipopolysaccharide as well as Interleukin-4, Interleukin-13 and AGE-RAGE signalling (Suppl. Figure 1). Many of those VitD targeted pathways were also targets of dexamethasone. These include pathways involved in inflammation; proliferation; pro-apoptosis, beside others (Figure S1).

VDR, NR3C1 and NR3C2 expression levels in different types of immune cells

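### The Results claim that vitamin D suppresses IL-17F preferentially and spares IL-17A, but the readable text gives no IL-17A result and no IL-17F versus IL-17A comparison to support it

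*Combined protocol and SAP*

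**What the plan says.** Primary outcome 4 is to "study the effects of Vitamin D on cytokines" at 8 weeks. It names no particular cytokine, no contrast and no selectivity hypothesis. The Statistical Analysis section says only that "Standard statistical t-tests and one-way ANOVA will be performed to test for statistical significance between data groups", with 0.05 as the threshold. It gives no equivalence margin, no comparison between cytokines and no multiplicity rule.

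The cytokine section of the Results lists six markers: "Blood levels of IL-17A, IL-17F, IFN- γ , IL-4, IL-5, and TNF- α were determined before and after VitD supplementation". It then states that "VitD preferentially suppressed the blood levels of IL-17F cytokine ($p=0.04$) without affecting IL-17A", and adds "while there was no significant difference in the placebo group ($p=0.17"). IL-4 is described separately: "A decrease in blood IL-4 cytokine levels was observed following treatment, however, not to a significant level ($p=0.07"). A closing sentence reports no significant effect on the remaining cytokines. No number for IL-17A appears in the text. The section refers to Figure 5, which is not available here.

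The arm sizes conflict. The Figure 3 legend gives 23 on vitamin D and 22 on placebo, while Table 1 gives 34 and 20. Both are used below.

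**The concern.** The sentence draws two separate conclusions.

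- **No effect on IL-17A.** This needs an estimate with an interval narrow enough to rule out a change that matters. A non-significant test alone does not provide that.
- **A larger effect on IL-17F than on IL-17A.** This needs a test of the difference between the two changes. Both are measured in serum from the same patients, so the test is feasible, but the text reports none.

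The apparent reasoning is that IL-17F crossed 0.05 and IL-17A did not. A difference in significance is not a significant difference. A reader could conclude that IL-17A is spared when the data may be compatible with an equal effect on both isoforms.

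**Working it through.** **What cannot be reproduced.** The p-value of 0.04 for IL-17F cannot be rebuilt, because the text gives no cytokine mean, SD, change or analysed number. The steps below are illustrations. They assume normally distributed changes and paired, two-sided 5% tests. The correlation between the two isoforms' changes is not given, so a range is shown.

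**Step 1. Standardised change implied by p = 0.04** (if it is a before/after test within the vitamin D arm): d = t/√n.

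- n = 23: t(22) = 2.183, so d = 2.183/√23 = 0.455 SD.
- n = 34: t(33) = 2.138, so d = 2.138/√34 = 0.367 SD.

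**Step 2. How often an equal effect gives the reported pattern.** Give both isoforms the same true change of 0.455 SD at n = 23 and simulate both tests.

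| Correlation of changes | IL-17A non-significant, given IL-17F significant | IL-17F alone significant, all trials |
|---|---|---|
| 0 | about 45% | about 25% |
| 0.5 | about 31% | about 17% |
| 0.7 | about 24% | about 13% |

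The first column of results is the relevant one once IL-17F is known to be significant. At n = 34 with d = 0.367 the results agree to within about 1 percentage point.

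**Step 3. Power against a fixed change.** Step 2 takes its effect from the p-value itself, so it hardly depends on sample size. For an assumed change of 0.5 SD (SD of the change), the noncentral t distribution with noncentrality 0.5√n gives a miss rate of 37% at n = 23 and 19% at n = 34.

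**Step 4. What a non-significant IL-17A result could leave open.** At n = 23 the 95% half-width is t(0.975, 22)/√23 = 0.432 SD. Suppose, for illustration only, that IL-17A fell with p = 0.5. The interval for its fall would run from about −0.29 to 0.58 SD, which includes the 0.455 implied for IL-17F.

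**Step 5. Can the direct contrast be recovered?** With equal variances of the standardised changes, z = (z_F − z_A)/√(2(1 − ρ)), where z_F = 2.054 for p = 0.04. If both isoforms fell:

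| IL-17A p (assumed) | ρ = 0 | ρ = 0.5 | ρ = 0.8 |
|---|---|---|---|
| 0.051 | 0.94 | 0.92 | 0.87 |
| 0.5 | 0.33 | 0.17 | 0.029 |
| 0.99 | 0.15 | 0.041 | 0.001 |

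The p-value of the contrast runs from 0.94 to 0.001 over inputs that the text does not report. The printed numbers do not settle the question in either direction.

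**The case against.** The strongest reply is that Figure 5 may show IL-17A values with almost no change, and that selectivity may be real. Both are possible, and Step 5 includes cases in which a direct test would succeed. The missing figure is not a fault of the document. The point is therefore limited to the readable text and the planned analysis. Plotted IL-17A values alone would still not be a test of the difference.

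Several stronger readings are tempting, and the documents do not support them.

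- **That the claim was demonstrably made from two within-arm tests.** The text does not label p = 0.04 as within-arm. That is inferred from the before/after wording and the separate placebo p-value. That IL-17A missed 0.05 is also inferred.
- **That the paragraph treats equal evidence unequally**, calling IL-4 a decrease and IL-17A unaffected. The IL-17A change is not given and may have been near zero, so different wording may be justified.
- **That equal effects would give this pattern in half of trials.** About 50% (correlation 0) is the chance that exactly one isoform, either one, is significant. IL-17F alone accounts for about 25%.
- **That the 45% miss rate shows the sample is too small.** It is observed power, a restatement of p = 0.04: about 43% at n = 10 and 46% at n = 200. Only the 0.5-SD figures in Step 3 depend on sample size, and 0.5 SD is an assumption.

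It is also fair to say that selectivity was never a prespecified hypothesis and is one clause among six cytokine results. That limits the weight of the point but does not supply the missing evidence.

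**Conclusion.** The point holds in a limited form. The readable text supports neither the absence of an effect on IL-17A nor a larger effect on IL-17F. It reports no IL-17A figure and no contrast between the isoforms, and none was planned. It does not follow that vitamin D acts equally on both. The claim is unsupported, not refuted.

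The size rests on the assumptions stated above. With an equal true effect at the size implied by p = 0.04, a significant IL-17F result would be accompanied by a non-significant IL-17A result in roughly a quarter to just under a half of trials. For an assumed 0.5-SD change, the IL-17A test would miss it in 37% of trials at n = 23 or 19% at n = 34. This affects one interpretive statement under a primary outcome, and not the validity of the trial. It is worth correcting because it changes what the trial is said to have found.

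**What to change.** 1. Delete the words 'preferentially' and 'without affecting IL-17A' from the cytokine section of the Results.
2. Report the IL-17A and IL-17F effects, each as an estimate with a 95% interval and the number of patients analysed.
3. For IL-17A, write: no significant change in IL-17A detected; a change as large as that seen for IL-17F is not excluded. Omit the second half only if the interval does exclude it.
4. If selectivity is still of interest, compute for each patient the log change in IL-17F minus the log change in IL-17A, and compare this between vitamin D and placebo. Label it post hoc and exploratory, because results are already known. Give its interval, and state that six cytokines were tested without a multiplicity rule. For scale, six independent tests at 0.05 carry a family-wise error of 1 − 0.95⁶ = 26.5%.

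The cost is one reworded sentence, two intervals and, optionally, one further analysis of data already collected. The downside is that the isoform-selective statement is weakened or dropped.
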